8.3.2. Outcomes

8.3.2.1. Safety events of interest

Safety events of interest to be assessed in the general population, immunocompromised individuals, individuals with a history of COVID-19, and pregnant women, and their risk

PFIZER CONFIDENTIAL CT24-WI-GL02-RF02 3.0 Non-Interventional Study Protocol Template For Secondary Data Collection Study 20-May-2021

Page 67 of 120

interval definitions, are listed in Table 8. Throughout the protocol, these safety events are referred to as "general safety events."

Safety events of interest include myocarditis/pericarditis and other outcomes being monitored in rapid-cycle analysis of COVID-19 vaccines in the FDA's BEST System (Wong et al., 2021) and the CDC's VSD (Shimabukuro, 2021a), with the addition of vaccine-associated enhanced respiratory disease (Munoz et al., 2021), immune hemolytic anemia, and thromboembolic events with thrombocytopenia. Other safety events of interest may be added as the understanding of the safety profile of Pfizer-BioNTech original monovalent COVID-19 Vaccine evolves and feasibility of their assessment permits in the data sources.

Table 8.General safety events to be assessed in the general population,
immunocompromised individuals, individuals with a history of COVID-
19, and pregnant women

Organ system	Safety event of interest	Risk window (days following receipt of Pfizer-BioNTech original monovalent COVID-19 Vaccine) ^a
Cardiac	Myocarditis/pericarditis	1-21 ^b
	Acute myocardial infarction	1-28
Neurologic	Acute disseminated encephalomyelitis	1-42
	Bell's palsy	1-42
	Convulsions	1-42
	Encephalomyelitis/encephalitis	1-42
	Guillain-Barré syndrome	1-42
	Narcolepsy	1-180
	Transverse myelitis	1-42
Hematologic	Deep vein thrombosis	1-28
	Disseminated intravascular coagulation	1-28
	Immune hemolytic anemia	1-42
	Immune thrombocytopenia	1-42

PFIZER CONFIDENTIAL

CT24-WI-GL02-RF02 3.0 Non-Interventional Study Protocol Template For Secondary Data Collection Study 20-May-2021 Page 68 of 120

Table 8.General safety events to be assessed in the general population,
immunocompromised individuals, individuals with a history of COVID-
19, and pregnant women

Organ system	Safety event of interest	Risk window (days following receipt of Pfizer-BioNTech original monovalent COVID-19 Vaccine) ^a
	Pulmonary embolism	1-28
	Thromboembolic events associated with thrombocytopenia	1-28
	Thrombotic thrombocytopenic purpura	1-28
	Venous thromboembolism	1-28
	Hemorrhagic stroke	1-28
	Ischemic stroke	1-28
Respiratory	Acute respiratory distress syndrome	1-28
	Vaccine-associated enhanced respiratory disease	1-365
Other system	Anaphylaxis	0-1
	Appendicitis	1-42
	Kawasaki disease	1-42
	Multisystem inflammatory syndrome	1-42

COVID-19 = coronavirus disease 2019.

a. Time interval following vaccination when individuals will be followed for safety events of interest. Day 0 refers to the day of vaccination.

b. Sensitivity analysis will assess alternative risk interval definitions of 1-7 and 1-14 days.

The following pregnancy safety outcomes will be assessed in pregnant women or their infants:

- Spontaneous abortion: spontaneous pregnancy loss before 20 completed weeks gestation, identified using diagnosis codes
- Stillbirth: fetal deaths at or after 20 completed weeks gestation, identified using diagnosis codes

PFIZER CONFIDENTIAL

CT24-WI-GL02-RF02 3.0 Non-Interventional Study Protocol Template For Secondary Data Collection Study 20-May-2021 Page 69 of 120

- Preterm birth: live birth before 37 completed weeks gestation, identified using diagnosis codes
- Major congenital malformations: major congenital malformations will be identified in live-born infants using code lists from the National Birth Defects Prevention Network (NBDPN, 2021a), which defines a major defect as a congenital abnormality that requires medical or surgical treatment, has a serious adverse effect on health and development, or has significant cosmetic impact (NBDPN, 2021b)
- Small size for gestational age: less than 10th percentile of weight for gestational age, identified using diagnosis codes for small size for gestational age

8.3.2.2. Outcome identification and validation

Safety events of interest will be identified with a date of diagnosis in data from claims or electronic health records (where available, as not all data research partners will have access to electronic health records) using predefined algorithms based on codes for diagnoses (with codes for procedures and/or treatments if appropriate for the outcome). As possible, validated algorithms will be used. Detailed algorithm definitions (including washout periods to define incident events and the medical care settings in which safety events will be identified) and code lists will be included in the SAP.

Algorithms for myocarditis/pericarditis will be validated for individuals aged 12 years and older. Algorithms for other outcomes that have signaled in other studies or surveillance systems may also be validated if the outcomes could be susceptible to substantial misclassification. The determination of whether each outcome is susceptible to substantial misclassification will be informed by clinical expert opinion and review of prior validation studies, if available. For the outcomes selected for validation, clinician review of medical records or patient profiles (i.e., listings of codes in data from claims or electronic health records in chronological order) will be conducted on a sample of cases to estimate the positive predictive values of case-finding algorithms and to estimate the proportion of cases that were accurately identified as occurring during the risk interval. To the greatest extent possible, such reviews will be conducted without knowledge of vaccination status. Clinical definitions of safety events of interest will be based on Brighton Collaboration definitions, where available, or other clinical definitions from published literature if medical record review is implemented.

For safety events of interest selected for algorithm validation, a sampling strategy that considers the rarity of events may be used to identify cases that will undergo clinician review. The sampling strategy, selection of safety events for which algorithms will be validated and rationale for the selection, details on the methods for validation (including criteria for determining whether algorithms have performed adequately), and the plan for integrating the validation results into final analysis will be described separately in a data validation plan. Details of sensitivity analyses (quantitative bias analysis) to adjust for potential misclassification based on results from validation will be described in the SAP.

PFIZER CONFIDENTIAL

CT24-WI-GL02-RF02 3.0 Non-Interventional Study Protocol Template For Secondary Data Collection Study 20-May-2021 Page 70 of 120

8.3.3. Covariates

Covariates will be identified in claims and electronic health records (where available, as not all data research partners will have access to electronic health records) using administrative health plan enrollee data or codes for diagnoses (with procedures or medications, as appropriate). Detailed algorithms and code lists to identify each covariate will be included in the SAP.

8.3.3.1. Potential confounding variables

The following variables will be used to describe the overall study population, immunocompromised individuals, individuals with a history of COVID-19, and pregnant women and will be considered as potential confounding variables to be included in propensity score models for analysis of general safety events.

- Demographics will be evaluated at the index date for each individual, unless otherwise noted
- Age: Individuals of all ages will be included in the study; for descriptive analyses, age categories will be 0-4, 5-11, 12-15, 16-20, 21-29, 30-49, 50-64, 65-80, and greater than 80 years
- Sex
- Geographic region (zip code where available, state or census region; evaluated using the latest information available on the index date)
- Race/ethnicity: Data on race/ethnicity are anticipated to be incomplete, and the feasibility of including this variable in the analyses will be assessed before study start
- Date of Pfizer-BioNTech original monovalent COVID-19 Vaccine (categorized as appropriate, e.g., by year or month)
- Dose of vaccine received (e.g., 1, 2, 3)
- Comorbidities, identified in the 12 months before the index date (unless otherwise noted) in claims or electronic health records using diagnosis codes (with procedure and/or pharmacy dispensing codes as appropriate)
 - History of anaphylaxis (not including the index date)
 - History of allergies
 - Diabetes mellitus (type 1, type 2, or gestational diabetes in current pregnancy)
 - Hypertension

PFIZER CONFIDENTIAL

CT24-WI-GL02-RF02 3.0 Non-Interventional Study Protocol Template For Secondary Data Collection Study 20-May-2021 Page 71 of 120

- Cardiovascular disease
- Cerebrovascular disease
- Chronic respiratory disease
- Chronic kidney disease
- Chronic liver disease
- Cancer
- Epilepsy
- Autoimmune disorders
- Influenza and other respiratory infections (including COVID-19)
- Gastrointestinal infections
- Immunocompromising conditions, including the following (to be defined in more detail in the SAP):
 - Immunodeficiencies
 - Immunosuppressant medication use
 - Human immunodeficiency virus and other immunosuppressing conditions
 - Receipt of organ or bone marrow transplant
- Obesity (to be identified with proxies using diagnosis and procedure codes; capture anticipated to be incomplete)
- Preeclampsia/eclampsia (captured only in subgroup analysis of pregnant women)
- Pregnancy status (on the index date), identified using an algorithm as described in Section 8.2.3
- Medications in the 12 months before and including the index date, identified in data from claims or electronic health records via procedure and/or pharmacy dispensing codes
 - Analgesics

PFIZER CONFIDENTIAL

CT24-WI-GL02-RF02 3.0 Non-Interventional Study Protocol Template For Secondary Data Collection Study 20-May-2021 Page 72 of 120

- Antibiotics
- Antiviral medications
- Corticosteroids
- Nonsteroidal anti-inflammatory drugs
- Psychotropics
- Statins
- Novel oral anticoagulants
- Warfarin
- Non-COVID-19 vaccinations (including those administered concomitantly with Pfizer-BioNTech original monovalent COVID-19 Vaccine) in the 12 months before or on the index date, identified in data from claims or electronic health records with procedure and/or pharmacy dispensing codes
 - Influenza
 - Pneumococcal disease
 - Diphtheria, tetanus, and pertussis
 - Polio
 - Measles, mumps, and rubella
 - Haemophilus influenzae type b
 - Hepatitis B virus
 - Human papillomavirus
 - Meningitis
 - Rotavirus
 - Varicella
 - Herpes zoster

CT24-WI-GL02-RF02 3.0 Non-Interventional Study Protocol Template For Secondary Data Collection Study 20-May-2021 Page 73 of 120

- Healthcare utilization (including telehealth encounters, if feasible) in the 12 months before or on the index date
 - Any healthcare encounter
 - Hospitalizations
 - Emergency department visits
 - Skilled nursing facility, nursing home, or extended care facility stay
 - Cancer screening(s)
 - Other preventive healthcare services, as appropriate
 - COVID-19 tests

The following variables will be used to describe the population of pregnant women and will be considered as potential confounders to be included in propensity score models for analysis of pregnancy safety outcomes. Except where noted, only information up to and including the index date will be used to identify potential confounders.

- Demographics: maternal age (on the index date), geographic region (using the latest information available as of the index date), race/ethnicity (if feasible, on the index date)
- Comorbidities, identified in the 12 months before the index date in claims or electronic health records using diagnosis codes (with procedure and/or pharmacy dispensing codes as appropriate).
 - Diabetes mellitus (type 1, type 2)
 - Hypertension
 - Connective tissue disorders
 - Thyroid disorders
 - Heart disease
 - Epilepsy and mood disorders
 - Asthma
 - Liver disease

PFIZER CONFIDENTIAL

CT24-WI-GL02-RF02 3.0 Non-Interventional Study Protocol Template For Secondary Data Collection Study 20-May-2021 Page 74 of 120

- Kidney disease
- Cancer
- Obesity, identified in the 12 months before the index date, with proxies based on diagnosis and procedure codes (capture anticipated to be incomplete since documentation via diagnosis or procedure codes is not routinely done in claims data)
- Alcohol use, identified in the 12 months before the index date, with proxies based on diagnosis and procedure codes (capture anticipated to be incomplete)
- Smoking, identified in the 12 months before the index date, with proxies based on diagnosis and procedure codes (capture anticipated to be incomplete)
- Multiple pregnancy, identified during pregnancy via diagnosis codes. Information recorded after the index date will be used to identify potential confounders
- Gestational diabetes, identified during pregnancy via diagnosis codes
- Preeclampsia/eclampsia, identified during pregnancy via diagnosis codes
- Gestational hypertension
- TORCH infections (toxoplasmosis, other [syphilis, varicella-zoster, parvovirus B19], rubella, cytomegalovirus, and herpes infections), identified during pregnancy via diagnosis codes
- Teratogenic medications from 28 days before pregnancy up to and including the end of pregnancy, identified via pharmacy dispensing and procedure codes
- Vaccinations other than COVID-19 vaccinations (including those administered concomitantly with Pfizer-BioNTech original monovalent COVID-19 Vaccine) from 28 days before pregnancy up to and including the end of pregnancy, identified via pharmacy dispensing and procedure codes

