 - Comorbidities (in the 12 months before and not including the index date): diabetes mellitus (type 1, type 2), hypertension, gestational hypertension, connective tissue

PFIZER CONFIDENTIAL

CT24-WI-GL02-RF02 3.0 Non-Interventional Study Protocol Template For Secondary Data Collection Study 20-May-2021 Page 22 of 120 disorders, thyroid disorders, heart disease, epilepsy and mood disorders, asthma, liver disease, kidney disease, cancer

- Obesity (in the 12 months before the index date; capture anticipated to be incomplete since obesity is not routinely documented via diagnosis or procedure codes in claims data)
- Alcohol use and smoking (in the 12 months before or on the index date; capture anticipated to be incomplete)
- Pregnancy complications (recorded during the pregnancy): multiple pregnancy, gestational diabetes, preeclampsia/eclampsia, TORCH infections (toxoplasmosis, other [syphilis, varicella-zoster, parvovirus B19], rubella, cytomegalovirus, and herpes infections); except for multiple pregnancy, only information recorded up to and including the index date will be used to identify potential confounders
- Teratogenic medications (from 28 days before pregnancy up to and including the end of pregnancy); only information up to and including the index date will be used to identify potential confounders
- Non-COVID-19 vaccinations, including those administered concomitantly with Pfizer-BioNTech original monovalent COVID-19 Vaccine (from 28 days before pregnancy up to and including the end of pregnancy); only information up to and including the index date will be used to identify potential confounders

Data sources

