8.7.2.3. Methods for addressing confounding

8.7.2.3.1. General population, immunocompromised individuals, and individuals with a history of COVID-19

Analysis of nonpregnant populations will use matching on age, sex, state (if feasible, or broader geographic region if not feasible), and time–specific propensity scores within the data from each data research partner to account for confounding. The propensity score is the predicted probability of an individual being in the exposed cohort rather than in the corresponding unexposed cohort, given a set of observed covariates. Additionally, analysis of third doses received more than 2 months after the second dose will also match on time since receipt of the second dose.

8.7.2.3.1.1. Analysis of general safety events following primary series

Among the general population, immunocompromised individuals, and individuals with a history of COVID-19, the risk of general safety events will be compared among individuals who have received at least the first dose in a primary series of Pfizer-BioNTech original monovalent COVID-19 Vaccine versus those among individuals who have not received any COVID-19 vaccine during a concurrent time. In individuals aged 6 months through 4 years, these analyses will include doses 1, 2, and 3. Details for handling the timing between individual doses in this age group will be described in the SAP. In individuals aged 5 years and older, these analyses will include dose 1 and dose 2, as well as dose 3 if a third dose is received within 2 months of the second dose.

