Estimation of propensity scores will be performed for the dose 1, 2, and 3 (if applicable) cohorts combined. However, matching of exposed to unexposed individuals will be done separately for the dose 1 exposed cohort, the dose 2 exposed cohort, and the dose 3 exposed cohort within narrow time periods to account for changing predictors of vaccination over time, seasonality of circulating infections, and changes in healthcare utilization over time. Matching will occur by age and state (if feasible, or broader geographic region if not feasible) within each time period and dose number. The matching and propensity score estimation process will be done first for the general population and then will be repeated separately for immunocompromised individuals and for individuals with a history of COVID-19. Propensity score estimation will be conducted within each data research partner. The steps for propensity score modeling and matching are as follows.

a. Within each data research partner, the study period will be divided into 1-month intervals of calendar time ("time intervals"). All individuals who received a vaccine dose— whether dose 1, dose 2, or dose 3—during the considered month would contribute vaccinated index dates during the time interval; if an individual received more than 1 dose during a calendar month, all eligible index dates will be included as independent observations in the propensity score model. All individuals with at least 1 unexposed

PFIZER CONFIDENTIAL

CT24-WI-GL02-RF02 3.0 Non-Interventional Study Protocol Template For Secondary Data Collection Study 20-May-2021 Page 92 of 120 person-day in the time interval will have an unvaccinated index date randomly assigned during all unexposed person-time within the time interval. In this context, "unexposed person-day" refers to a day in which the individual has no record of COVID-19 vaccine on or before that day.

- b. Within each time interval, the propensity to be vaccinated will be estimated among all individuals with index dates within the time interval using logistic regression. The dependent variable for the logistic regression model will be vaccination status, and the independent variables will be baseline covariates (i.e., individual characteristics as described in Section 8.3.3). The model will combine dose 1, dose 2, and dose 3 index dates, which assumes that the factors influencing an individual's likelihood of being vaccinated does not change between dose 1, dose 2, and dose 3.

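### The candidate confounder list for general safety events omits smoking, although the protocol already derives a code-based smoking proxy for pregnancy outcomes

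*Protocol*

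**What the plan says.** Protocol Section 8.3.3.1 lists covariates separately by type of outcome.

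- **General safety events.** These variables "will be considered as potential confounding variables to be included in propensity score models for analysis of general safety events". The list covers demographics, comorbidities, medications, other vaccinations and healthcare use. It includes "Obesity (to be identified with proxies using diagnosis and procedure codes; capture anticipated to be incomplete"), but neither smoking nor alcohol use.
- **Pregnancy safety outcomes.** This list contains "Smoking, identified in the 12 months before the index date, with proxies based on diagnosis and procedure codes (capture anticipated to be incomplete") and "Alcohol use, identified in the 12 months before the index date, with proxies based on diagnosis and procedure codes (capture anticipated to be incomplete").

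The abstract (Section 3) shows the same split: "Alcohol use and smoking (in the 12 months before or on the index date; capture anticipated to be incomplete") appears only among the covariates for pregnancy outcomes.

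Section 8.3.3 leaves algorithms and code lists to the SAP, but names the variables in the protocol. Section 8.7.2.3 says of the propensity model that "the independent variables will be baseline covariates (i.e., individual characteristics as described in Section 8.3.3"). On the use of the score it says: "Analysis of nonpregnant populations will use matching on age, sex, state (if feasible, or broader geographic region if not feasible), and time–specific propensity scores".

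Acute myocardial infarction, ischemic and hemorrhagic stroke and acute respiratory distress syndrome are general safety events with 1-28 day windows (Table 8).

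**The concern.** The primary design compares vaccinated people with people who have no record of any COVID-19 vaccine. Matching on demographics and the propensity score is its control of confounding. Smoking bears on several of the cardiovascular and respiratory outcomes and may differ by vaccination status. If it remains more common among the unvaccinated after matching, it pulls the relative risk down. In a safety study that direction hides harm.

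The protocol accepts residual confounding in Section 8.9 on the ground that the data will not hold every confounder. That ground does not fit here, because a smoking proxy is already to be built from the same kind of data. Nor does the protocol say why the proxy serves one set of outcomes and not the other.

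**Working it through.** **1. The plan's own precision figure.** Section 8.5 gives a 92% probability that the upper 95% limit is below 2.5 for myocarditis/pericarditis. The inputs are 5,000,000 vaccinated, 2 doses each, 10 per 100,000 person-years, 21 days, true RR 1.4 and 1:1 matching.

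- e0 = 5,000,000 × 2 × (21/365.25) × 10/100,000 = 57.5; e1 = 1.4 × 57.5 = 80.5
- SE(log RR) = √(1/57.5 + 1/80.5) = 0.173
- P = Φ(ln(2.5/1.4)/0.173 − 1.96) = 0.919, which agrees with 0.92

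The same model reproduces Table 9 rows for myocardial infarction: 0.952 against 0.95 (500,000, RR 1.0, limit 1.5) and 0.557 against 0.56 (5,000,000, RR 1.4, limit 1.5).

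**2. Precision for myocardial infarction** (Table 9: 208 per 100,000 person-years, 28 days, 5,000,000 vaccinated).

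- e0 = 5,000,000 × 2 × (28/365.25) × 208/100,000 = 1,594.5 per arm
- SE at RR 1.0 = √(2/1,594.5) = 0.0354
- Null 95% interval = exp(±1.96 × 0.0354) = 0.93 to 1.07

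**3. Bias from leaving smoking out.** All smoking inputs are assumptions: post-matching prevalence pE among the vaccinated and pU among the unvaccinated, and smoking rate ratio R, with nothing absorbed by listed covariates.

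Bias factor B = [1 + pE(R − 1)] / [1 + pU(R − 1)]. The probability that a true null gives an upper limit below 1 is Φ(−ln B/SE − 1.96), with SE = √(1/e0 + 1/(e0·B)). Without bias it is 2.5%.

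| pE / pU | R | B | P(upper limit < 1), 5,000,000 vaccinated |
|---|---|---|---|
| 12% / 15% | 1.5 | 1.060/1.075 = 0.986 | 6% |
| 12% / 16% | 2 | 1.12/1.16 = 0.966 | 16% |
| 12% / 20% | 2 | 1.12/1.20 = 0.933 | 48% |
| 12% / 20% | 3 | 1.24/1.40 = 0.886 | 91% |

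For the 12%/20%, R = 2 row, the probability is 9% at 500,000 vaccinated and 97% at 20,000,000.

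**4. What an incomplete code recovers.** Take 12%/20% and R = 2, match on the code, and assume no false positives.

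- *50% sensitivity in both groups.* Of the vaccinated, 6% carry a code. Among unvaccinated people without a code, 0.10/0.90 = 11.1% smoke. B = 1.12/(0.06 × 2 + 0.94 × 1.111) = 1.12/1.164 = 0.962. Since ln 0.962/ln 0.933 = 0.56, about 44% of the log bias is removed, and the 48% falls to about 19%.
- *50% in the vaccinated, 30% in the unvaccinated.* Now 0.14/0.94 = 14.9% of uncoded unvaccinated people smoke. B = 1.12/(0.12 + 0.94 × 1.149) = 1.12/1.20 = 0.933, so nothing is gained.
- *The same unequal sensitivities at 12%/16%.* B = 1.12/(0.12 + 0.94 × 1.118) = 0.957, slightly worse than the 0.966 from omission.

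**The case against.** **The list is not closed.** The variables are to be considered, propensity-score details go to the SAP, and Section 8.7 lets the SAP modify the plans. A reader might infer a locked model, and the text does not support that. What stands is narrower: smoking is not among the named candidates for these outcomes.

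**Incomplete capture may be the unstated reason.** The Version 4.0 amendment log removed reproductive history because claims record it incompletely. That is possible, but it sits badly with keeping obesity under the same caveat.

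**The size is assumed throughout.** The imbalance must survive matching on age, sex, region and a monthly score that can include cardiovascular, cerebrovascular and chronic respiratory disease, hypertension, diabetes, statins, cancer screening and preventive care. This stands. The figures above are upper bounds for their inputs, and the 48% row uses a wide imbalance.

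**The proxy may not help.** Smoking codes are recorded at encounters and may be captured differently by exposure group. Matching on healthcare use should lessen this but cannot guarantee a gain.

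**The self-controlled risk interval (SCRI) analysis addresses time-constant confounding.** Its 42-day limit admits the named 1-28 day events, and it may become the primary design. As written, though, it is a sensitivity analysis with outcomes still to be named. For vaccine-associated enhanced respiratory disease, with its 365-day window, Section 8.9 says that neither the SCRI nor the historical cohort is feasible.

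**Pregnant women.** A reader might infer that smoking, "Multiple pregnancy, identified during pregnancy via diagnosis codes" and gestational hypertension are left out of their general safety analyses. Section 8.7.2.3.2.1 instead describes one propensity process for general and pregnancy outcomes, drawing on all of Section 8.3.3. Set against the split in Section 8.3.3.1, this is an ambiguity, not a proven omission.

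**Conclusion.** The omission is real and appears in both the body and the abstract. Its consequence is a forgone partial adjustment in the primary cohort relative risks for smoking-related general safety events.

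Under assumed post-matching prevalences of 12% against 15-20% and a smoking rate ratio of 1.5-3, a null relative risk would read about 0.99 to 0.89 before any absorption by listed proxies. At the milder end this is small beside the 0.93-1.07 null interval for myocardial infarction at 5,000,000 vaccinated. At the wider end it exceeds the half-width. The downward direction depends on smoking being more common among the unvaccinated, which the protocol neither states nor excludes.

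It would be tempting to conclude that these relative risks are known to be confounded, or that false protective findings are likely. The documents give no smoking prevalence or effect size, so neither follows. The calculation covers smoking and myocardial infarction only; no effect of alcohol, multiple pregnancy or gestational hypertension is quantified.

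**What to change.** 1. In Section 8.3.3.1 and the abstract, add the smoking proxy already defined for pregnancy outcomes to the candidate covariates for general safety events, at least in adults. Add the alcohol proxy with lower priority.
2. Report the balance of the proxy in the matched cohorts with the other covariates.
3. In Section 8.7.2.3.2.1, state that the covariates listed for pregnancy outcomes also apply to general safety events in pregnant women.
4. Align the look-back for smoking and alcohol: the abstract includes the index date, while the items in Section 8.3.3.1 refer only to the period before it.
5. Keep the residual-confounding caveat and the SCRI analysis, because the proxy is incomplete, may be captured differently by exposure group, and adjusts only in part.

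The cost is a few lines of text and reuse of code lists that the pregnancy analyses need anyway.
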